## **10.4 DOSE MODIFICATIONS**

Patients who have had treatment interruptions due to reasons other than DLTs may restart daily dosing at the same dose at the discretion of the investigator when the toxicity has resolved to Grade  $\leq 1$  or baseline; however, any patients whose treatment is interrupted for an adverse event that is related to study drug and who do not restart treatment within 28 days will be withdrawn from study treatment.

For patients experiencing a DLT, treatment should be held until the severity of the toxicity decreases to Grade  $\leq 1$  or baseline. If they are deriving clinical benefit, patients may be restarted on study drug at the next lower dose level that has been tested in a previous cohort, at the discretion of the investigator and in consultation with the Sponsor. For Phase Ia and Phase IIa, no more than 2 dose reductions of GDC-0810 will be allowed.

For Phase Ib Cohort C1 a maximum of two dose reductions of GDC-0810 and palbociclib will be allowed. No dose reductions are planned for the LHRH agonists (Cohort D1). GDC-0810 dose reductions should be managed without changing regimen, for example, patients in Phase Ia who were being treated on a BID regimen will dose reduce to the next lower GDC-0810 dose level but still administered as BID. Similarly, Phase Ia patients who were being treated without a fasting requirement will dose reduce to the next lower dose level but still administered without a fasting requirement.

Doses reduced for drug-related toxicity should generally not be re-escalated. However, intrapatient re-escalation back to the previous dose level may be permitted at the discretion of the investigator and in consultation with the Sponsor.

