### **10.2.2 Phase IIa**

DLT definitions are not applicable for the Phase IIa dose expansion portion of the study.

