### **10.4.1 Dose Modifications for Phase Ia, Ib Cohort D, and IIa**

During the Phase Ia dose escalation DLT evaluation period, dose modifications will not be permitted; however, dose interruptions can be instituted for patient safety purposes. In Cycle 1, any interruption  $> 7$  days due to an adverse event assessed as related to GDC-0810 will meet the criteria for DLT.

After the DLT evaluation period is concluded and/or during the Phase IIa portion of the study, dose interruptions and/or reductions to the next lower dose level will be permitted as needed, provided that study discontinuation criteria have not been met (e.g., documented disease progression or unacceptable toxicity).

In Cohort D, no dose modification of the LHRH agonist will be permitted. However, the dose of GDC-0810 may be reduced in Cohort D1 or D2 on the basis of joint review by Sponsor and study investigators of available safety and tolerability data observed during the DLT assessment window.

GDC-0810 *must* be held in the presence of the following toxicities potentially attributed to the study drug:

- Decrease in post-treatment glomerular filtration rate (GFR) of more than 25% as compared to baseline
- Any other Grade  $\geq 3$  adverse events potentially attributed to the study drug

GDC-0810 dose reductions may occur in increments of 200 mg. Therefore, the possible GDC-0810 doses permitted in Phase IIa are 600 mg, 400 mg, and 200 mg. Because no more than two dose reductions are permitted, patients should discontinue GDC-0810 if they experience adverse events at 200 mg of GDC-0810 requiring dose reduction.

Adverse events should be managed as shown in [Table 4](#).

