**Table 4 Dose Modification and Management Guidelines (cont.)**

Toxicity	Dose Modification and Management Guidelines
Diarrhea (cont.):	
Grade 2	

• Manage with adequate anti-diarrheal agents (e.g., loperamide) and maximum supportive care according to local standards and practices.

• Closely monitor for resolution.

• Hold treatment with GDC-0810 until resolution to ≤Grade 1.

• If Grade 2 diarrhea is recurrent after improvement to Grade 1, despite maximum medical management, reduce GDC-0810 by one dose level.

• Upon resolution, if Grade 2 diarrhea is recurrent with no alternate etiology, consider starting loperamide 2 mg 1–2 times daily as secondary prophylaxis (i.e. use of loperamide to prevent further diarrhea).

Grade $\geq 3$	

• Manage with adequate anti-diarrheal agents (e.g., loperamide) and maximum supportive care according to local standards and practices.

• Closely monitor for resolution.

• Hold treatment with GDC-0810 until resolution to ≤Grade 1.

• At resolution of first occurrence, reduce the dose of GDC-0810 by one dose level on improvement to Grade ≤1.

• At resolution of second occurrence, reduce dose of GDC-0810 by one dose level on improvement to Grade ≤1.

• On third occurrence, discontinue GDC-0810.

• At any occurrence of Grade 4 diarrhea, consider discontinuation of GDC-0810.

• Upon resolution, consider starting loperamide 2 mg 1–2 times daily as secondary prophylaxis (i.e., use of loperamide to prevent further diarrhea).

AEI=adverse event of special interest

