**Table 4 Dose Modification and Management Guidelines (cont.)**

Toxicity	Dose Modification and Management Guidelines
Nausea and/or Vomiting:	
General	

Grade <math>\geq 2</math> vomiting and Grade <math>\geq 3</math> nausea are identified as AESIs requiring expedited reporting from study sites regardless of seriousness.

Grade 1–2	

Manage with anti-emetics and supportive care according to local standards and practices. If persistent despite maximal medical therapy, hold treatment with GDC-0810 until resolution to Grade <math>\leq 1</math>.

Grade $\geq 3$	

Manage with anti-emetics and supportive care.

Hold treatment with GDC-0810 until resolution to Grade <math>\leq 1</math>.

Reduce GDC-0810 dose by one dose level when treatment resumes.

Venous Thromboembolic Events (including Pulmonary Embolism):	
General	

Patients should be advised to seek immediate medical attention if they become aware of any symptoms of pulmonary embolism (PE) or deep vein thrombosis (DVT), such as acute onset of chest pain, shortness of breath, or swelling in extremities.

Grade <math>\geq 2</math> VTEs are identified as AESIs requiring expedited reporting from study sites regardless of seriousness.

Grade 1–2	

Manage and treat patients according to institutional guidelines and local standards of care.

May consider anti-coagulation and/or inferior vena cava (IVC) filter based upon local best standards and practices after an individual assessment of risk benefit for each patient.

Grade $\geq 3$	

As Grade 1–2.

Hold dosing with GDC-0810 until the patient is stable.

Discuss with study Medical Monitor for appropriate dose modification and management.

AESI=adverse event of special interest

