#### **10.4.2 Dose Modifications for Phase Ib Cohort C1**

During the dose escalation DLT evaluation period, dose modifications will not be permitted; however, dose interruptions can be instituted for patient safety purposes. In Phase Ib Cohort C1, any grade non-hematologic toxicity assessed as related to GDC-0810 and/or palbociclib that leads to study drug interruption of  $> 7$  days' duration will meet the criteria for DLT. Patients who miss  $\geq 7$  doses of GDC-0810 or  $\geq 5$  doses of palbociclib during the DLT evaluation period due to reasons other than a DLT will be replaced.

After the DLT evaluation period is concluded, dose interruptions and/or reductions to the next lower dose level will be permitted as needed, provided that study discontinuation criteria have not been met (e.g., documented disease progression or unacceptable toxicity). Dose modification guidelines for treatment-related non-hematologic and hematologic toxicities are shown in [Table 5](#) and [Table 6](#), respectively.

GDC-0810 dose reductions may occur in decrements of 200 mg. Therefore, the possible GDC-0810 doses permitted in Phase Ib Cohorts C1 and C2 are 600 mg, 400 mg, and 200 mg. Because no more than two dose reductions are permitted, patients should discontinue GDC-0810 if they experience adverse events at 200 mg of GDC-0810 requiring dose reduction.

Palbociclib dose reductions may occur in decrements of 25 mg. Therefore, the possible palbociclib doses permitted in Phase Ib Cohorts C1, C2 and C3 are 125 mg, 100 mg, and 75 mg. Palbociclib dose de-escalation below 75 mg/day is not allowed, but in consultation with the sponsor, the schedule may be changed for example to 75 mg/day 2 weeks on followed by 2 weeks off (2/2 schedule).

Both GDC-0810 and palbociclib *must* be held in the presence of the following toxicities potentially attributed to the study drug:

- Decrease in post-treatment GFR of more than 25% as compared to baseline
- Any other Grade  $\geq 3$  non-hematologic adverse events potentially attributed to the study drug.

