Grade $\geq 3$ diarrhea	

Manage with adequate anti-diarrheal agents (e.g., loperamide) and maximum supportive care according to local standards and practices.

Closely monitor for resolution.

Withhold GDC-0810 and palbociclib until symptoms resolve to Grade <math>\leq 1</math>.

At resolution of first occurrence, reduce the dose of GDC-0810 by one dose level on improvement to Grade <math>\leq 1</math>. Consider reducing palbociclib by one dose level.

At resolution of second occurrence, reduce dose of GDC-0810 by one dose level on improvement to Grade <math>\leq 1</math>. Consider reducing palbociclib by one dose level.

On third occurrence, discontinue GDC-0810

At any occurrence of Grade 4 diarrhea, consider discontinuation of GDC-0810.

Upon resolution, consider starting loperamide 2 mg 1–2 times daily as secondary prophylaxis (i.e., use of loperamide to prevent further diarrhea).

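### The same-dose restart clause in Section 10.4 conflicts with the reductions directed in Tables 4 and 5, and the two-reduction scheme does not fit Cohort C1's 400 mg start

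*Combined protocol and SAP*

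**What the plan says.** Section 10.4 splits the restart rule by the reason for interruption. If the reason was not a DLT, patients "may restart daily dosing at the same dose at the discretion of the investigator" once the toxicity is back to Grade 1 or lower or to baseline. After a DLT, "patients may be restarted on study drug at the next lower dose level that has been tested in a previous cohort". Section 10.2.2 adds: "DLT definitions are not applicable for the Phase IIa dose expansion portion of the study".

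Section 10.4.1 (Phase Ia, Cohort D and Phase IIa) says "Adverse events should be managed as shown in" Table 4. For Grade 3 or higher diarrhea, Table 4 reads "At resolution of first occurrence, reduce the dose of GDC-0810 by one dose level on improvement to Grade" 1 or lower, then a further one-level reduction at the second occurrence and discontinuation at the third. For Grade 3 or higher nausea or vomiting it reads "Reduce GDC-0810 dose by one dose level when treatment resumes". It also directs a one-level reduction for Grade 2 diarrhea that recurs despite maximum management.

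Table 5 (Cohort C1) likewise directs a reduction after a first Grade 3 or higher diarrhea or nausea/vomiting, and refers Grade 2 diarrhea back to Section 10.4.1. At the second Grade 3 or higher diarrhea it says "At resolution of second occurrence, reduce dose of GDC-0810 by one dose level on improvement to Grade" 1 or lower; discontinuation comes at the third.

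For Cohort C1, Section 10.4 caps reductions of GDC-0810 and palbociclib at two. Section 10.4.2 sets 200 mg decrements, lists 600, 400 and 200 mg for Cohorts C1 and C2, and cites the two-reduction limit as the reason that "patients should discontinue GDC-0810 if they experience adverse events at 200 mg of GDC-0810 requiring dose reduction".

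**The concern.** Two instructions on the same event point to different doses. In Phase IIa, a Grade 3 diarrhea interruption cannot be a DLT, so the same-dose permission applies on its face, while Table 4 directs a lower dose. In Cohort C1, a patient already at 200 mg meets a further reduction step in one place and a discontinuation rule in another.

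What is at stake is mainly the handling of patients still being dosed. Enrollment has stopped, but those with clinical benefit may continue. There is also a reporting consequence. Section 14 counts dose modifications outside the protocol specifications as violations, so one action can be compliant under one passage and a violation under another. Section 15.3 flags dose modifications and summarizes discontinuations, and those outputs would mix patients handled under different rules.

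**Working it through.** **Part 1: same dose or lower dose.** There is no arithmetic here; the question is which events fall under both passages.

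- The same-dose clause covers non-DLT interruptions: all of Phase IIa (Section 10.2.2), events after the DLT window in Phases Ia and Ib, and, in Cohorts C1 and D1, Grade 3 nausea, vomiting or diarrhea excepted from DLT because it falls to Grade 2 or lower within 24 hours (Section 10.2.3).
- The tables direct a GDC-0810 reduction after Grade 3 or higher diarrhea, after Grade 3 or higher nausea/vomiting, and for recurrent Grade 2 diarrhea (Table 4, to which Table 5 refers). They direct none for venous thromboembolism, vaginal hemorrhage or raised transaminases.
- The overlap is the three listed events when they are not DLTs. For these, one passage permits the same dose and the other directs a lower one. No sentence sets an order of precedence. Both tables are titled as guidelines, and the text of Section 10.4.1 describes reductions as permitted where needed.

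**Part 2: the Cohort C1 dose ladder.** Inputs: start 400 mg (Section 10.1.3.1); step 200 mg and lowest listed dose 200 mg (Section 10.4.2); cap of two reductions (Section 10.4).

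Reductions available = (start − lowest listed dose) / step

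- 600 mg start: (600 − 200) / 200 = 2. This reproduces the stated ladder of 600, 400, 200 mg.
- 400 mg start: (400 − 200) / 200 = 1. The stated two reductions are not reproduced.
- Palbociclib: (125 − 75) / 25 = 2, consistent with the cap.

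Applying the Table 5 steps for Grade 3 or higher diarrhea:

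| Start | Occurrence | Dose at event | Table 5 | Section 10.4.2 |
|---|---|---|---|---|
| 600 mg | 1 | 600 mg | reduce to 400 | reduction available |
| 600 mg | 2 | 400 mg | reduce to 200 | reduction available |
| 600 mg | 3 | 200 mg | discontinue | discontinue |
| 400 mg | 1 | 400 mg | reduce to 200 | reduction available |
| 400 mg | 2 | 200 mg | reduce (200 − 200 = 0, not a listed dose) | discontinue |
| 400 mg | 3 | not reached if 10.4.2 governs | discontinue | not applicable |

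From 600 mg the two sources agree throughout. From 400 mg they part at the second occurrence. A C1 patient could have two steps only after moving up to 600 mg, which requires that level to have passed DLT evaluation in a previous cohort (Section 10.1.3.1); Cohort C2, the 600 mg combination level, will not enroll.

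**The case against.** The strongest reply to Part 1 is that a general permission stands beside a specific rule. Section 10.4 mandates nothing, and Section 10.4.1 sends sites to Table 4. A site that reduces after Grade 3 diarrhea complies with both passages. The permission still has work to do where the tables direct no reduction, such as a first Grade 2 diarrhea. The Grade 2 and Grade 3 or higher diarrhea rows are also in italics, which Version 9 uses for substantive new text, so they look like the current instruction. This is a sensible reading, but the protocol does not state it. A site that restarts at the same dose can cite express investigator discretion in Section 10.4, so the missing precedence statement remains.

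On Part 2, two is a ceiling and not a promise, and it covers palbociclib, which does have two steps. The 600/400/200 list was written for C1 and C2 together. The 200 mg rule is triggered by an event that requires a reduction, so Table 5 and Section 10.4.2 can be read in sequence: the table calls for a reduction, none is listed, and the floor rule takes over. Much of this stands, and it rules out calling the two passages irreconcilable. It does not explain why Table 5 reserves discontinuation for a third occurrence, or why Section 10.4.2 rests the 200 mg rule on two reductions when only one is available from 400 mg.

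The consequences are also bounded. No confirmatory inference is planned (Section 15.1), and dose modifications are flagged individually, so mixed handling would be visible.

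**Conclusion.** This is an internal inconsistency in wording that should be corrected because it bears on patients still on treatment. It has two parts: no stated precedence between Section 10.4 and the reductions directed in Tables 4 and 5, and a two-reduction scheme that does not fit a 400 mg start.

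Three stronger readings are tempting and are not supported.

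- A reader might infer that all of the roughly 100 Phase IIa patients are affected. They are the patients whom the clause governs; the conflict arises only in those with the listed events while on treatment. Section 1.1 gives related rates of any grade (diarrhea 44% and nausea 38% in Phase IIa) but none for Grade 3 or higher, so the number is unknown.
- A reader might infer that a C1 patient at 200 mg is flatly told both to reduce and to discontinue. Section 10.4.2 can be read as overriding Table 5.
- A reader might extend this to any second gastrointestinal event. For second-occurrence Grade 3 or higher nausea/vomiting, Table 5 allows the reduction to fall on palbociclib instead, so that case is not clearly in conflict.

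The C1 case is therefore a second Grade 3 or higher diarrhea after one reduction, in a cohort for which Section 1.1 reports 4 patients. The approximately 5 in Section 15.2.3 pools C0 and C1. The documents do not say whether any such event occurred. The ladder result assumes that 200 mg is the lowest dose for this cohort, as Section 10.4.2 lists.

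**What to change.** Reconcile the Section 10.4 restart clause with the Table 4 and Table 5 entries for Grade 3 or higher diarrhea, Grade 3 or higher nausea/vomiting and recurrent Grade 2 diarrhea, and add a sentence saying which governs when they differ. Reconcile the two-reduction allowance in Section 10.4 and the rationale in Section 10.4.2 with Table 5's second- and third-occurrence diarrhea steps for a patient who started at 400 mg. The clinical team decides what the rule should be; this review takes no position on it. For reporting, record which passage was followed for any such event already handled, so that violation status and the dose-modification listings can be interpreted. The cost is protocol wording, with no change to sample size or analysis.

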### **10.4.1 Dose Modifications for Phase Ia, Ib Cohort D, and IIa**

During the Phase Ia dose escalation DLT evaluation period, dose modifications will not be permitted; however, dose interruptions can be instituted for patient safety purposes. In Cycle 1, any interruption  $> 7$  days due to an adverse event assessed as related to GDC-0810 will meet the criteria for DLT.

After the DLT evaluation period is concluded and/or during the Phase IIa portion of the study, dose interruptions and/or reductions to the next lower dose level will be permitted as needed, provided that study discontinuation criteria have not been met (e.g., documented disease progression or unacceptable toxicity).

In Cohort D, no dose modification of the LHRH agonist will be permitted. However, the dose of GDC-0810 may be reduced in Cohort D1 or D2 on the basis of joint review by Sponsor and study investigators of available safety and tolerability data observed during the DLT assessment window.

GDC-0810 *must* be held in the presence of the following toxicities potentially attributed to the study drug:

- Decrease in post-treatment glomerular filtration rate (GFR) of more than 25% as compared to baseline
- Any other Grade  $\geq 3$  adverse events potentially attributed to the study drug

GDC-0810 dose reductions may occur in increments of 200 mg. Therefore, the possible GDC-0810 doses permitted in Phase IIa are 600 mg, 400 mg, and 200 mg. Because no more than two dose reductions are permitted, patients should discontinue GDC-0810 if they experience adverse events at 200 mg of GDC-0810 requiring dose reduction.

Adverse events should be managed as shown in [Table 4](#).

**Table 4 Dose Modification and Management Guidelines**

Toxicity	Dose Modification and Management Guidelines
Gastrointestinal Toxicities:	
General	

• Patients should be closely monitored for gastrointestinal (GI) symptoms and their effects on their wellbeing. Patients experiencing nausea, vomiting, and diarrhea should be treated and managed per standard of care and per protocol guidelines, including use of anti-diarrheal agents and appropriate supportive care including hydration and dietary modification if clinically indicated.

• Remind patients to take GDC-0810 30 minutes after the largest meal of the day (preferably the evening).

Diarrhea:	
General	
At first report of any grade diarrhea:
 

• Initiate loperamide 4 mg, followed by 2 mg after each unformed stool. Daily dose should not exceed local recommendations in any 24-hour period.

• Infectious or alternate etiology should be excluded.

• Grade <math>\geq 2</math> diarrhea is identified as an AESI requiring expedited reporting from study sites regardless of seriousness.

Grade 1	

• Manage with adequate anti-diarrheal agents (e.g., loperamide) and maximum supportive care according to local standards and practices.

• Closely monitor for resolution.

• If diarrhea does not resolve after 14 consecutive days, hold GDC-0810 until complete resolution of diarrhea.

• Upon resolution, if Grade 1 diarrhea had persisted for > 1 week with no alternate etiology, consider starting loperamide 2 mg 1–2 times daily as secondary prophylaxis (i.e., use of loperamide to prevent further diarrhea).

AESI=adverse event of special interest

**Table 4 Dose Modification and Management Guidelines (cont.)**

Toxicity	Dose Modification and Management Guidelines
Diarrhea (cont.):	
Grade 2	

• Manage with adequate anti-diarrheal agents (e.g., loperamide) and maximum supportive care according to local standards and practices.

• Closely monitor for resolution.

• Hold treatment with GDC-0810 until resolution to ≤Grade 1.

• If Grade 2 diarrhea is recurrent after improvement to Grade 1, despite maximum medical management, reduce GDC-0810 by one dose level.

• Upon resolution, if Grade 2 diarrhea is recurrent with no alternate etiology, consider starting loperamide 2 mg 1–2 times daily as secondary prophylaxis (i.e. use of loperamide to prevent further diarrhea).

Grade $\geq 3$	

• Manage with adequate anti-diarrheal agents (e.g., loperamide) and maximum supportive care according to local standards and practices.

• Closely monitor for resolution.

• Hold treatment with GDC-0810 until resolution to ≤Grade 1.

• At resolution of first occurrence, reduce the dose of GDC-0810 by one dose level on improvement to Grade ≤1.

• At resolution of second occurrence, reduce dose of GDC-0810 by one dose level on improvement to Grade ≤1.

• On third occurrence, discontinue GDC-0810.

• At any occurrence of Grade 4 diarrhea, consider discontinuation of GDC-0810.

• Upon resolution, consider starting loperamide 2 mg 1–2 times daily as secondary prophylaxis (i.e., use of loperamide to prevent further diarrhea).

AEI=adverse event of special interest

**Table 4 Dose Modification and Management Guidelines (cont.)**

Toxicity	Dose Modification and Management Guidelines
Nausea and/or Vomiting:	
General	

Grade <math>\geq 2</math> vomiting and Grade <math>\geq 3</math> nausea are identified as AESIs requiring expedited reporting from study sites regardless of seriousness.

Grade 1–2	

Manage with anti-emetics and supportive care according to local standards and practices. If persistent despite maximal medical therapy, hold treatment with GDC-0810 until resolution to Grade <math>\leq 1</math>.

Grade $\geq 3$	

Manage with anti-emetics and supportive care.

Hold treatment with GDC-0810 until resolution to Grade <math>\leq 1</math>.

Reduce GDC-0810 dose by one dose level when treatment resumes.

Venous Thromboembolic Events (including Pulmonary Embolism):	
General	

Patients should be advised to seek immediate medical attention if they become aware of any symptoms of pulmonary embolism (PE) or deep vein thrombosis (DVT), such as acute onset of chest pain, shortness of breath, or swelling in extremities.

Grade <math>\geq 2</math> VTEs are identified as AESIs requiring expedited reporting from study sites regardless of seriousness.

Grade 1–2	

Manage and treat patients according to institutional guidelines and local standards of care.

May consider anti-coagulation and/or inferior vena cava (IVC) filter based upon local best standards and practices after an individual assessment of risk benefit for each patient.

Grade $\geq 3$	

As Grade 1–2.

Hold dosing with GDC-0810 until the patient is stable.

Discuss with study Medical Monitor for appropriate dose modification and management.

AESI=adverse event of special interest

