**Table 5 Dose Modification Guidelines for Treatment-Related Non-Hematologic Toxicities (cont.)**

Toxicity	Palbociclib and/or GDC-0810 Dose Modification
Nausea and or Vomiting:	
General and Grade 1	See Section 10.4.1.
Grade $\geq 2$ nausea or vomiting	

If persistent despite maximal medical therapy, withhold GDC-0810 until recovery to Grade <math>\leq 1</math>. If no improvement is noted in palbociclib combination patient, consider additionally withholding palbociclib until recovery to Grade <math>\leq 1</math>.

Grade $\geq 3$ nausea or vomiting	

Manage with anti-emetics and supportive care.

Withhold GDC-0810 and/or palbociclib until symptoms resolve to Grade <math>\leq 1</math>.

On resolution of first occurrence, reduce dose of GDC-0810 by one dose level when treatment resumes and consider reducing dose of palbociclib.

On resolution of second occurrence, reduce dose of GDC-0810 and/or palbociclib by one dose level when treatment resumes.

Venous thromboembolic events (including pulmonary embolism):	
General and Grade 1–2	See Section 10.4.1.
Grade $\geq 3$ venous thromboembolic events (including pulmonary embolism)	

Withhold GDC-0810 and palbociclib until patient is stable and consult with Sponsor before resuming treatment.

Vaginal hemorrhage:	
General and Grade 1	See Section 10.4.1.
Grade $\geq 2$ vaginal hemorrhage	

Withhold GDC-0810 and palbociclib until Grade <math>\leq 1</math> and consult with Sponsor before resuming treatment.

Grade $\geq 3$ non-hematologic toxicity	

Withhold GDC-0810 and/or palbociclib until symptoms resolve to Grade <math>\leq 1</math> or Grade <math>\leq 2</math> (after discussion with Medical Monitor).

If repeated toxicity is seen in the next cycle or if recovery from Grade 3 is delayed beyond 7 days discuss with Medical Monitor.

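### Two nausea/vomiting hold instructions are internally inconsistent: the Grade 1 hold in Table 4 is released by the grade that triggers it, and three texts differ for Grade ≥3 events in Cohort C1

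*Combined protocol and SAP*

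**What the plan says.** Section 10.4.1, Table 4, governs Phase Ia, Phase IIa and Cohort D. Its nausea/vomiting block has two action rows. The Grade 1–2 row calls for anti-emetics and supportive care, then: "If persistent despite maximal medical therapy, hold treatment with GDC-0810 until resolution to Grade" ≤1. The Grade ≥3 row holds GDC-0810 with no persistence condition, releases at Grade ≤1, and adds: "Reduce GDC-0810 dose by one dose level when treatment resumes". For Grade 1 diarrhea the same table uses a different release state: "hold GDC-0810 until complete resolution of diarrhea".

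Section 10.4.2, Table 5, governs Cohort C1. For Grade 1 nausea/vomiting it says only "See Section 10.4.1". Two further rows follow:

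- The row labelled "Grade $\geq 2$ nausea or vomiting": "If persistent despite maximal medical therapy, withhold GDC-0810 until recovery to Grade" ≤1. If there is no improvement, withholding palbociclib as well is to be considered.
- The row labelled "Grade $\geq 3$ nausea or vomiting": "Withhold GDC-0810 and/or palbociclib until symptoms resolve to Grade" ≤1. There is no persistence condition, and dose-reduction steps follow on resolution.

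The text of Section 10.4.2 that introduces Table 5 requires both GDC-0810 and palbociclib to be held for a fall in GFR of more than 25% and for any other Grade ≥3 non-hematologic event potentially attributed to the study drug.

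**The concern.** A dose-hold rule needs a trigger and a release state that the triggering event does not already satisfy. It also needs one rule per grade. The Table 4 row fails the first test for Grade 1. The Cohort C1 text fails the second for Grade ≥3.

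These are live instructions. Version 9 keeps patients with clinical benefit on treatment and states that the dose modification guidelines were updated. Section 1.1 names nausea and vomiting as two of the three identified risks of GDC-0810. How a hold is read has consequences elsewhere in the plan. Section 10.4 withdraws patients who do not restart within 28 days of a related interruption, and it caps dose reductions at two. Section 14 counts dose modifications outside the protocol's specifications as violations. Section 15.3 has dose modifications flagged in the listings. If sites resolve the wording differently, the same event can be recorded as an interruption, as no interruption, or as a departure from protocol.

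**Working it through.** No arithmetic decides this point. The check reads each rule as grade range, hold trigger and release state, and then asks two questions. Does any grade in a row already meet that row's release state when the hold starts? Does any grade fall under more than one instruction with different terms?

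**Table 4 (Phase Ia, Phase IIa, Cohort D)**

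| Grade | Hold trigger | Release | Result |
|---|---|---|---|
| 1 | persistent despite maximal therapy | Grade ≤1 | already met at entry; hold has no effect |
| 2 | persistent despite maximal therapy | Grade ≤1 | coherent |
| ≥3 | none beyond the grade | Grade ≤1, then one dose level down | coherent |

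Section 10.4 does not repair the Grade 1 line. Its general restart condition is Grade ≤1 or baseline, which a Grade 1 event also meets.

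**Cohort C1 (Table 5 and the text of Section 10.4.2)**

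| Grade | Text that applies | Persistence needed to hold GDC-0810? | Palbociclib |
|---|---|---|---|
| 1 | cross-reference to Section 10.4.1 | as Table 4 | Table 4 is silent |
| 2 | Table 5, Grade ≥2 row | yes | consider, if no improvement |
| ≥3 | Table 5, Grade ≥2 row (no upper limit) | yes | consider, if no improvement |
| ≥3 | Table 5, Grade ≥3 row | no | withheld with, or instead of, GDC-0810 |
| ≥3 | Section 10.4.2 text | no | hold mandatory, with GDC-0810 |

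Grade 1 inherits the Table 4 problem, and Grade 2 is coherent. Grade ≥3 falls under three instructions that differ on two things: whether persistence is required, and which drugs are held. Table 5's closing row for Grade ≥3 non-hematologic toxicity in general has no persistence condition either. It uses the same either-or-both wording, so it does not settle the second difference.

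The overlap is not the table's usual style. Table 5's diarrhea rows are Grade 2 and Grade ≥3, and its Grade ≥3 diarrhea row withholds both drugs, in line with Section 10.4.2.

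**Size.** Section 1.1 gives any-grade related nausea at the 9 September 2016 cut. The 38% is attributed to Phase IIa, but the set described is 107 patients, six of them from Cohort D1. That gives 0.38 × (107 − 6) = 38.4 to 0.38 × 107 = 40.7, or about 38 to 41 patients. In Cohort C1 it is 0.75 × 4 = 3 patients. None of these counts is split by grade or persistence, and the number still on treatment under Version 9 is not stated. They show that nausea is common, not how many patients met either inconsistency.

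**The case against.** The case on the other side has four parts.

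**The Table 5 overlap is answered by other text.** A reader might infer that, for a Grade 3 event, a site complies equally by holding or by waiting for maximal therapy to fail. The documents do not support that. Section 10.4.2 makes the hold mandatory for Grade ≥3 non-hematologic events potentially attributed to study drug, and the more specific Grade ≥3 row has no persistence condition. This part of the objection stands, and it reduces the overlap to an ambiguity of labelling. It does not remove the difference over which drugs are held. Holding both satisfies every text. Holding one is allowed by Table 5's Grade ≥3 row but not by Section 10.4.2.

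**Most of the rules work.** A reader might infer that the nausea/vomiting hold rules as a whole cannot be followed. That is too strong, because only the persistent Grade 1 instruction defeats itself. Nor does the text create a hold without end, since it states an end that is already reached. One could call the Grade 1 instruction merely redundant. Even so, a row that tells the site to hold and at the same moment permits restart should say which is meant. The Grade 1 diarrhea row shows that the table can use a release state below the entry grade. It does not show what the nausea rule should be.

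**The counts are not affected patients.** A reader might take the roughly 41 and 3 as the size of the problem. They are any-grade nausea counts, and the number affected could be zero.

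**The consequences are limited.** Enrollment has stopped, Section 15.1 plans no confirmatory inference, and the tables are titled as guidelines. All of that is true and bears on priority. Patients remaining on treatment are still dosed under these rows.

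**Conclusion.** The point holds in a limited form. First, Table 4's release condition for persistent Grade 1 nausea/vomiting is the state in which the event enters the row, so the hold has no effect at Grade 1. Cohort C1 inherits this by cross-reference. Second, for Grade ≥3 nausea/vomiting in Cohort C1, Table 5's two rows and the text of Section 10.4.2 give differing instructions on the persistence condition and on which drugs are held.

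The second part assumes that the events are potentially attributed to GDC-0810, which Section 9 defines as the study drug, because that is the condition in Section 10.4.2. It also assumes that the word other in that list is relative to the GFR item beside it, so nausea and vomiting are included.

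The number of patients affected cannot be derived from the documents. No effect on sample size, power, error rates or any endpoint is claimed. What is at stake is consistent dosing conduct and consistent interruption and reduction records among patients still on treatment. Which clinical rule is right is not a question this review answers.

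**What to change.** Reconcile Table 4, Table 5 and the text of Section 10.4.2 so that three conditions hold:

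1. The Table 4 instruction for Grade 1 nausea/vomiting no longer has a release condition identical to its entry state. The Table 5 cross-reference will then carry the corrected wording into Cohort C1.
2. Each grade maps to exactly one Table 5 nausea/vomiting row.
3. The Table 5 Grade ≥3 nausea/vomiting row and Section 10.4.2 agree on which drugs are held.

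Making the rows mutually exclusive is not enough alone, because it would leave the third conflict in place. The sponsor's medical team decides which action applies to which grade.

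The cost is the wording of a few table rows and one list in an amendment or clarification. No data collection, sample size or analysis changes.
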